### 9.3.2. Unsolicited Adverse Events

The proportion of subjects reporting at least one unsolicited adverse event will be summarized by MedDRA system organ class (SOC) and preferred term (PT).

Unsolicited adverse events by subject will be presented in [Listing 12](#).

The following summaries for unsolicited adverse events will be presented:

- Subject incidence and total frequency of adverse events over time by MedDRA SOC, PT, and treatment group with 95% CI (Days 1-8 Days > 8) ([Table 55](#), [Table 56](#), [Table 57](#), and [Table 58](#));

- Summary of severity and relationship to study product by MedDRA SOC, PT and treatment group ([Table 59](#) and [Table 60](#));
- Subject incidence and total frequency of pregnancy-or infancy related adverse events by treatment group with 95% CI ([Table 77](#) and [Table 78](#));
- Subject listing of non-serious adverse events of moderate or greater severity by MedDRA SOC, PT, and treatment group ([Table 63](#));
- Listing of new onset chronic medical conditions by MedDRA SOC, PT, and treatment group ([Table 64](#));
- Bar chart of the frequency of serious and non-serious related adverse events by severity, MedDRA SOC, and treatment group ([Figure 227](#));
- Bar chart of the incidence of serious and non-serious related adverse events by maximum severity, MedDRA SOC, and treatment group ([Figure 228](#) )

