7.5. Final Study Visit

6 months Postpartum Safety Follow-up Visit, Birth + Day 180 (± 7 d): Clinic Visit, Postpartum Women and Infants (Visit 08 or V08)

- Obtain interim medical history of mother and infant. Study personnel will solicit and record all new congenital anomalies and SAEs on the appropriate data collection form.
- Study personnel will record infant concomitant medications on the appropriate data collection form.
- A targeted physical examination may be performed by a study clinician licensed to make medical diagnoses and listed on the Form FDA 1572 as the site principal investigator or sub-investigator, if indicated based on review of interim medical history. A targeted physical exam may be performed on the mother, infant, or both.
- 5 mL of infant venous blood will be collected for serology assessments.
- Approximately 30 mL of venous blood will be collected from the mother for post-vaccination serology and cytokine assays.
- 10-20 mL breast milk will be collected from the mother for antibody measurements.
- Study personnel will collect infant length, weight, and head circumference as well as birth outcomes on the appropriate data collection form.
- Study personnel will discharge mother and infant from study.

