9.3. Reporting Procedures

Solicited injection site and systemic reactogenicity events for pregnant women will be documented and reported from the time of each study vaccination through 7 days after the study vaccination.

Unsolicited non-serious AEs for pregnant women will be documented and reported from the time of study vaccination through approximately 30 days after the study vaccination (Day 31 or delivery, whichever occurs first, for pregnant women).

SAEs among pregnant women will be documented and reported from the time of study vaccination through 6 months postpartum.

For infants, there are no solicited events. AEs and SAEs will be recorded from birth until the 180 days of life for the infant visit. Events that are not medically attended, or that are a part of routine infant health maintenance, will not be reported.

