9.4. Type and Duration of Follow-up of Subjects after Adverse Events

Non-serious AEs will be collected, assessed, and followed through resolution from the time of study vaccination through approximately 30 days after study vaccination. For pregnant women, this period extends from vaccination until Day 31 or delivery, whichever occurs earlier. All unresolved non-serious AEs will be followed through resolution even if this extends beyond the study-reporting period.

SAEs and new-onset chronic medical conditions will be collected, assessed, and followed from the time of study vaccination through resolution even if this extends beyond the study-reporting period. The reporting period extends from vaccination until 6 months postpartum (180 days of life for the infant visit) for pregnant women.

Resolution of an AE/SAE is defined as the return to pretreatment status or stabilization of the condition with the expectation that it will remain chronic.

Follow-up procedures, evaluations, and outcomes will be recorded on the appropriate data collection form.

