{} Targeted physical examination, if indicated based on review of complete or interim medical history. An examination performed by a pregnant woman's own obstetrical clinician may also provide data when a targeted exam is called for. An exam should be performed for both the mother and infant if indicated for pregnant women on and after birth.											
~Vital signs assessed on Day 1 (Visit 01) prior to the study vaccination will be considered as baseline and used to determine eligibility. For the birth visit, vital signs recorded for the mother as part of her delivery record may be used in lieu of study personnel performing vital sign measurements.											
~A physical examination performed as part of routine antenatal care or a study-specific brief exam may be used.											
~If within 30 days post vaccination.											
~ If within 8 days post vaccination.											
*SAEs and new-chronic onset medical conditions only after Day 31 or delivery, whichever occurs earlier.											
~Only medically attended AEs will be recorded.											
~ The first colostrum collection may occur within the first 4 days of life of the infant.											
~ Infant vital signs will include axillary temperature, heart rate, and respiratory rate.											
~ If not performed as routine care, these measurements, except for weight, may be taken by qualified members of the research team within 7 days of infant life. Weights will only be recorded when obtained at birth.											
~ Procedures will be performed on both mother and infant.											
~ Only infant height, weight, and head circumference will be recorded at these visits.											

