	Not Reported																		
Ecchymosis	None																		
	Mild																		
	Moderate																		
	Severe																		
	Not Reported																		
Erythema	None																		
	Mild																		
	Moderate																		
	Severe																		

Table 52: Number and Percentage of Maternal Subjects Experiencing Solicited Events by Symptom, Severity, Day Post Dosing, and Treatment Group – BOOSTRIX (continued)

BOOSTRIX (N=X)																			
Symptom	Severity	Pre-Dose		Post-Dose		Day 2		Day 3		Day 4		Day 5		Day 6		Day 7		Day 8	
		n	%	n	%	n	%	n	%	n	%	n	%	n	%	n	%	n	%
	Not Reported																		
Induration	None																		
	Mild																		
	Moderate																		
	Severe																		
	Not Reported																		
Ecchymosis Measurement (mm)	None																		
	Mild																		
	Moderate																		
	Severe																		
	Not Reported																		
Erythema Measurement (mm)	None																		
	Mild																		
	Moderate																		
	Severe																		
	Not Reported																		
Induration Measurement (mm)	None																		
	Mild																		
	Moderate																		
	Severe																		
	Not Reported																		
Note: N = Number of subjects in the Maternal Safety Population randomized to receive intrapartum BOOSTRIX. Severity is the maximum severity reported post dosing for each subject for each day.																			

Tables with Similar Format:

**Table 53: Number and Percentage of Maternal Subjects Experiencing Solicited Events by Symptom, Severity, Day Post Dosing, and Treatment Group – Td**

**Table 54: Number and Percentage of Subjects Experiencing Solicited Events by Symptom, Severity, Day Post Dosing, and Treatment Group – All Subjects**

**14.3.1.2 Unsolicited Adverse Events****Table 55: Summary of Unsolicited Adverse Events by MedDRA System Organ Class and Preferred Term, and Treatment Group – BOOSTRIX – Maternal Subjects**

MedDRA System Organ Class	MedDRA Preferred Term	Day 1-8 Post Dose (N=X)				Days > 8 Post Dose (N=X)				Any Time (N=X)			
		n	%	95% CI	Events	n	%	95% CI	Events	n	%	95% CI	Events
Any SOC	Any PT	x	xx	xx, xx	x	x	xx	xx, xx	x	x	xx	xx, xx	x
[SOC 1]	Any PT												
	[PT 1]												
	[PT 2]												
[SOC 2]	Any PT												
	[PT 1]												
	[PT 2]												

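### SAP Tables 55-57: the open-ended Days > 8 and Any Time columns pool full and restricted AE collection, and no shell gives full SOC/PT incidence with CIs for non-serious AEs to Day 31

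*SAP*

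**What the plan says.** SAP 9.3.2 lists, for unsolicited AEs, "Subject incidence and total frequency of adverse events over time by MedDRA SOC, PT, and treatment group", with 95% CIs and the time split "Days 1-8 Days > 8". The Table 55 shell (BOOSTRIX mothers; Tables 56 and 57 share its format) has three column groups: Day 1-8, Days > 8 and Any Time. Each shows n, %, 95% CI and number of events by SOC and preferred term. The later period has no upper bound. SAP 9.3 puts every reported AE into the summaries and uses the whole population as denominator. Listing 12, the unsolicited AE listing, flags SAEs and new-onset chronic conditions, so both count as unsolicited AEs.

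Collection is narrower than these columns suggest. Protocol 9.3 ends non-serious unsolicited AE reporting at "Day 31 or delivery, whichever occurs first, for pregnant women". The same section says that "SAEs among pregnant women will be documented and reported from the time of study vaccination through 6 months postpartum". Protocol 9.4 adds that "SAEs and new-onset chronic medical conditions will be collected, assessed, and followed from the time of study vaccination". The footnote to the schedule in SAP Table 2 limits maternal recording to "SAEs and new-chronic onset medical conditions only after Day 31 or delivery, whichever occurs earlier". SAP 9.5 has pregnancy-related AEs collected for the whole study and displays them in Tables 77-82.

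The primary tolerability endpoint (SAP 3.2.1) is the frequency and severity of unsolicited non-serious AEs from vaccination to Day 31.

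**The concern.** One percentage with one CI should describe one ascertainment rule over one stated window. In the Days > 8 column, minor events can come only from Day 9 to Day 31 or delivery, while serious events and new chronic conditions can come from any day up to 6 months postpartum. Any Time has the same mixture, with Days 1-8 added. Nothing in the label tells the reader that non-serious collection has stopped.

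At stake is how the SOC/PT tables can be read. A preferred-term percentage under Days > 8 or Any Time is neither a Day 31 incidence nor an incidence over full follow-up. The endpoint that needs this breakdown is primary and is defined to Day 31, but none of the three columns ends there.

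**Working it through.** **Inputs.** Gestational age at vaccination is 14 0/7 to 26 6/7 weeks, or 98 to 188 days (Protocol 5.1). The final visit is 180 days after birth (Protocol 7.5). The Day 31 visit window is ±4 days, so Day 27 to Day 35 (Protocol 7.4.2.1). The documents give no expected gestational age at delivery, so it is assumed: 40 weeks as the main case, 28 to 42 weeks as the range.

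**Plan's own figure first.** The protocol summary gives maternal participation as approximately 10-13 months. With delivery at 40 weeks (280 days), pregnancy after vaccination lasts 280 − 188 = 92 to 280 − 98 = 182 days. Adding 180 days postpartum gives 272 to 362 days. Adding up to 30 days of screening gives 302 to 392 days, or 9.9 to 12.9 months at 30.4375 days per month. This reproduces the stated figure.

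**Length of the Days > 8 column.** With vaccination on Day 1 and P days from vaccination to delivery, delivery falls on Day 1 + P and follow-up ends on Day 1 + P + 180. The column therefore has P + 181 − 8 = P + 173 days. Full collection covers 31 − 8 = 23 of them, unless delivery comes first.

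**Share of the column under restricted collection** = (P + 173 − 23) / (P + 173):

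| Delivery (assumed) | Vaccinated 26 6/7 wk | Vaccinated 14 0/7 wk |
|---|---|---|
| 37 weeks | 221/244 = 90.6% | 311/334 = 93.1% |
| 40 weeks | 242/265 = 91.3% | 332/355 = 93.5% |
| 42 weeks | 256/279 = 91.8% | 346/369 = 93.8% |

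The protocol summary's own 3-7 months pregnant plus 6 months postpartum gives 244/267 = 91.4% to 366/389 = 94.1%.

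**Sensitivity.** The share is not above 90% in every case:
- Vaccinated at 26 6/7 weeks, delivery at 32 weeks: 186/209 = 89.0%, or 182/209 = 87.1% if the Day 31 visit falls on Day 35.
- Delivery on Day 31 itself: 180/203 = 88.7%.
- Vaccinated at 26 6/7 weeks, delivery at 40 weeks, Day 31 visit on Day 35: 238/265 = 89.8%.
- Vaccinated at 26 6/7 weeks, delivery at 28 weeks: 180/181 = 99.4%.

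**Which displays match the Day 31 window?**
- Table 45: one overall row for non-serious unsolicited AEs through Day 31, by arm.
- Table 59 note: one overall difference between arms with 95% CI, to Day 31. The body of the table gives SOC/PT by severity and relationship, but states no window or seriousness limit and has no CIs.
- Table 47: separates serious from non-serious events by SOC/PT, but covers only events at the 5% threshold, with no window and no CI.
- Tables 55-57: SOC/PT with CIs, but no column ending at Day 31 and no stated restriction to non-serious events.

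No shell combines full SOC/PT, CIs, non-serious events and the Day 31 window. The infant table cited in the same SAP bullet (Table 58) has no time columns and is not affected.

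**The case against.** The strongest reply is that this is a labelling matter in descriptive tables. The overall Day 31 proportion and arm difference are already planned, so a reader who inferred that the primary tolerability endpoint goes unreported would be wrong. The same collection rule applies to both blinded arms, so the BOOSTRIX-Td contrast is not biased. Protocol 11.4.2 expects few SAEs, so they may add little to the later column. Listing 12 and Tables 61, 63 and 64 would let a reader separate much of the mixture by hand. All of this stands.

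Two stronger readings are tempting, and the documents do not support either.

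- *The tables would show AEs clustering just after vaccination as an artefact of collection.* The shells show percentages, not rates per day. As an illustration, take a constant hazard fitted to the 17.8% 31-day incidence that Protocol 2.3.1 cites for BOOSTRIX in US adults aged 19 to 64, which is not this population. Then h = −ln(1 − 0.178)/31 = 0.00632 per day. Days 1-8 show 1 − exp(−8h) = 4.9%, and Days 9-31 alone show 1 − exp(−23h) = 13.5%. The later column would be the larger. An early excess appears only if someone divides by the full length of the column, which the SAP does not plan. Days 9-31 are also fully collected, so the column does contain real incidence.
- *The later period is SAE-only.* It is not. New-onset chronic conditions are recorded in it, and pregnancy-related AEs are collected throughout.

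The remaining gap is not answered: listings and two overall figures do not replace SOC/PT incidence with CIs for a defined window.

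**Conclusion.** The point holds as a mismatch between the display and the collection rule. The Days > 8 and Any Time columns pool two ascertainment regimes without saying so, and the SOC/PT breakdown with CIs is missing for the Day 31 tolerability window. Restricted collection takes up about 91%-94% of the Days > 8 column for term deliveries with a Day 31 cut-off, and about 87%-99% across the cases examined. These shares rest on an assumed delivery date; the 23 days of full collection follow from the documents, or 19 to 27 days across the visit window, fewer if delivery is earlier. No arm contrast and no overall primary tolerability figure changes. The change is worth making because the data are already collected and only table shells are affected.

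**What to change.** In SAP 9.3.2 and Tables 55-57, use these columns for non-serious unsolicited AEs: Days 1-8; Day 9 to Day 31 (or delivery if earlier); and total through Day 31 or delivery. Add a separate column, after Day 31 or delivery, restricted to SAEs and new-onset chronic conditions and labelled as such. An all-reported Any Time total may stay if a footnote states the collection rule. SAEs up to Day 31 remain in the Table 61 listing, as Protocol 11.4.2 intends, and in Any Time if it is kept. Pregnancy-related AEs stay in Tables 77-82.

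Cost: SAP wording and three table shells, with no new data. Four columns replace three, so each shell gains one column, or two if Any Time is kept.

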#### **9.4. Deaths, Serious Adverse Events and other Significant Adverse Events**

The following listing will be presented including Subject ID, Gestational Age/Infant Age, Adverse Event, Number of days post dose (duration), Reason Reported as an SAE, Relationship to Treatment, Alternate Etiology if not Related, and Outcome:

- Serious Adverse Events ([Table 61](#));
- Major Congenital Anomalies ([Table 62](#));
- Non-Serious, Unsolicited, Moderate or Severe Adverse Events ([Table 63](#));
- New Onset Chronic Medical Conditions ([Table 64](#))

#### **9.5. Pregnancies**

Every attempt was made to follow subjects to completion of pregnancy to document the outcome, including information regarding any complications with pregnancy and/or delivery. A table summarizing the total pregnancies, number of live births, and number of spontaneous abortions, elective abortions or still births by treatment group will be presented ([Table 75](#)). In addition, a listing of pregnancies and outcomes will be presented ([Listing 18](#), [Listing 19](#), [Listing 20](#), and [Listing 21](#)). A summary of infant size for gestational age at birth by treatment group will be presented in [Table 76](#) and [Figure 233](#).

Pregnancy related adverse events will be collected throughout the study and graded on a scale of 0 (absent), 1 (mild), 2 (moderate) and 3 (severe). Pregnancy related maternal events include pregnancy loss, bleeding during pregnancy or labor, postpartum hemorrhage, postabortal endometritis/salpingitis, preterm rupture of membranes, preterm contractions/labor/delivery, poor fetal growth, hypertension/preeclampsia/eclampsia, chorioamnionitis, postpartum endometritis, gestational diabetes and other pregnancy related AE. Infant events include preterm birth, birth weight, neonatal complications in a term infant, other AE in newborn and congenital abnormality/birth defect ([Table 8](#)).

The proportion of subjects reporting at least one pregnancy related adverse event will be summarized for each pregnancy related adverse event, any maternal symptom, and any infant symptom. The 95% CI will be calculated using Clopper-Pearson methodology from a binomial distribution (SAS Proc Freq with a binomial

(exact) option) will be presented ([Table 77](#) and [Table 78](#)). A Fisher's exact test w the difference in the proportion of subjects reporting a pregnancy related adverse event ([Table 79](#) and [Table 80](#)).

For each pregnancy related event, any maternal event, and any infant event, the maximum severity will be summarized for the maternal and infant Safety populations. The number and percentage of subjects reporting each event will be summarized by the maximum severity and treatment group. ([Table 81](#) and [Table 82](#)). The frequency of pregnancy- and infancy-related adverse events are presented in a bar chart in [Figure 229](#) and [Figure 231](#). The incidence of pregnancy- and infancy-related AEs are presented in [Figure 230](#) and [Figure 232](#).

A listing of all pregnancy or infancy related adverse events will be presented in [Listing 13](#).

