### 3.2. Endpoints

#### 3.2.1. Primary

##### Safety and Tolerability:

- Safety in pregnant women: Frequency and severity of study vaccine-related serious adverse events, and all SAEs in pregnant women from study vaccination through 6 months postpartum, description and comparison between those receiving BOOSTRIX and Td.
- Safety in pregnant women and fetuses/infants: Frequency and severity of adverse events specific to pregnancy, in pregnant women and their infants (as delineated in [Section 4.5.1](#) ), description and comparison between those receiving BOOSTRIX and Td.
- Tolerability in pregnant women: Frequency and severity of solicited injection site and systemic reactogenicity events from study vaccination until 7 days following vaccination (Day 8).
- Tolerability in pregnant women: Frequency and severity of all unsolicited non-serious AEs from day of study vaccination to Day 31, description and comparison between those receiving BOOSTRIX and Td.
- Safety in the infants: Frequency and severity of study vaccine-related serious adverse events, and all SAEs in infants from birth through 6 months of age, description and comparison between infants born to women vaccinated with BOOSTRIX and Td.

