## 5. SAMPLE SIZE CONSIDERATIONS

Based on the accrual rate for similar studies, it seems reasonable to expect that the sites will be able to enroll this study in a timely fashion. Prior experience suggests up to 15% of subjects may be excluded from the per protocol analysis for the primary immunogenicity outcome either because they were lost-to-follow-up or otherwise do not have data available following the study vaccination, or because they had a protocol deviation requiring their exclusion from the per protocol analysis.

The study is planned to enroll 200 pregnant women (133 BOOSTRIX, 67 Td) and their infants.

This will be one of the first studies of maternal Tdap vaccination in an African, low resource setting, and where infants received whole cell, rather than acellular pertussis vaccinations. Thus, this study is intended to obtain preliminary estimates of immune response in this setting; it is not designed to test a specific null hypothesis.

**Table 3** indicates the probability of observing one or more safety event, such as solicited injection site or systemic symptom, or an unsolicited adverse event of a particular type within a treatment arm.

In addition to safety, as a co-primary objective, the study will assess serum PT antibody at birth among infants whose mothers received a single dose of BOOSTRIX or Td, and as secondary and exploratory objectives, the study will assess maternal and infant humoral response to all vaccine antigens. Immune response will be measured by ELISA. **Table 4** presents the precision (95% confidence interval (CI)) available for estimating GMC of ELISA titers against the vaccine component using assumptions for GMC and standard deviation (SD) for maternal and infant response to Tdap from Munoz et al. [10] and infant response post third dose of primary DTwP vaccine series from Ladhani et al. [11]

**Table 5** presents the minimum difference in infant PT antibody GMC at birth between the Td and Tdap (BOOSTRIX) vaccination arms that would be detectable with 80% power. The assumed GMC and SD used for these calculations are based on the PT antibody GMC and SD observed at birth in infants whose mother received either Tdap or placebo vaccination during pregnancy, reported in Munoz et al. [10] The calculations are based on a two-sided two sample T-test to compare means, with alpha = 0.05.

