### 9.1. Demographic and Other Baseline Characteristics

Summaries of maternal age, ethnicity, other ethnic group, race, maternal age, and GA at vaccination will be presented by treatment group and overall in [Table 15](#) (categorical characteristics) and [Table 16](#) (continuous characteristics). Summaries of infant, sex, ethnicity, other ethnic group, race, GA at birth, delivery, Apgar score (1, 5 and 10 minutes), birth weight, length at birth, and head circumference at birth, will be presented by treatment group and overall in [Table 17](#) (categorical characteristics) and [Table 18](#) (continuous characteristics). Ethnicity is categorized as Hispanic or Latino, or not Hispanic and not Latino. In accordance with NIH reporting policy, subjects may self-designate as belonging to more than one race or may refuse to identify a race, the latter reflected in the case report form (CRF) as “No” to each racial option.

Individual subject listings ([Appendix 3](#)) will be presented for all demographics ([Listing 5](#) and [Listing 6](#)).

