**Table 18: Summary of Infant Continuous Demographic and Baseline Characteristics by Treatment Group**

Variable	Statistic	BOOSTRIX (N=X)	Td (N=X)	All Subjects (N=X)
Gestational Age at Delivery (days)	Mean	xx.x	xx.x	xx.x
	Standard Deviation	xx.x	xx.x	xx.x
	Median	xx.x	xx.x	xx.x
	Minimum	xx	xx	xx
	Maximum	xx	xx	xx
Birth Weight (kg)	Mean			
	Standard Deviation			
	Median			
	Minimum			
	Maximum			
Length (cm) at Birth	Mean			
	Standard Deviation			
	Median			
	Minimum			
	Maximum			
Head Circumference (cm) at Birth	Mean			
	Standard Deviation			
	Median			
	Minimum			
	Maximum			

Note: N= Number of subjects in the Infant Safety Population

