Preterm Contractions/Labor/Delivery	Proportion (95% CI)		
	Difference (95% CI)		
	p-value*		
Poor Fetal Growth	Proportion (95% CI)		
	Difference (95% CI)		
	p-value*		
Hypertension, Preeclampsia/eclampsia	Proportion (95% CI)		
	Difference (95% CI)		
	p-value*		
Chorioamnionitis	Proportion (95% CI)		
	Difference (95% CI)		
	p-value*		
Postpartum Endometritis	Proportion (95% CI)		
	Difference (95% CI)		
	p-value*		
Gestational Diabetes	Proportion (95% CI)		

Table 79: Comparison of the Proportion of Maternal Subjects Experiencing Pregnancy-Related Adverse Events by Symptom and Treatment Group (continued)

Symptom	Statistic	BOOSTRIX (N=X)	Td (N=X)
	Difference (95% CI)		
	p-value*		
Other Pregnancy Related AE	Proportion (95% CI)		
	Difference (95% CI)		
	p-value*		

Note: N = Number of subjects in the Maternal Safety Population.  
\*P-value is based on Fisher's exact test.

**Table 80: Comparison of the Proportion of Infant Subjects Experiencing Infancy-Related Adverse Events by Symptom and Treatment Group**

Symptom	Statistic	BOOSTRIX (N=X)	Td (N=X)
Any Neonatal and Infant Event	Proportion (95% CI)	x.xx (x.xx, x.xx)	x.xx (x.xx, x.xx)
	Difference (95% CI)	NA	x.xx (x.xx, x.xx)
	p-value*	NA	0.xxx
Preterm Birth	Proportion (95% CI)		
	Difference (95% CI)		
	p-value*		
Birth Weight	Proportion (95% CI)		
	Difference (95% CI)		
	p-value*		
Neonatal Complications in a Term Infant	Proportion (95% CI)		
	Difference (95% CI)		
	p-value*		
Other AE in Newborn	Proportion (95% CI)		
	Difference (95% CI)		
	p-value*		
Congenital Abnormalities/Birth Defect	Proportion (95% CI)		
	Difference (95% CI)		
	p-value*		

Note: N = Number of subjects in the Infant Safety Population.  
\*P-value is based on Fisher's exact test.

**Table 81: Number and Percentage of Maternal Subjects Experiencing Pregnancy-Related Events by Symptom, Maximum Severity, and Treatment Group**

Symptom	Severity	BOOSTRIX (N=X)			Td (N=X)			All Subjects (N=X)		
		n	%	95% CI	n	%	95% CI	n	%	95% CI
Any Maternal Pregnancy Related Symptom	None	x	xx	x.x, x.x	x	xx	x.x, x.x	x	xx	x.x, x.x
	Mild									
	Moderate									
	Severe									
Pregnancy Loss	None									
	Mild									
	Moderate									
	Severe									
Bleeding	None									
	Mild									
	Moderate									
	Severe									
Postpartum Hemorrhage	None									
	Mild									
	Moderate									
	Severe									
Postabortal endometritis/salpingitis	None									
	Mild									
	Moderate									
	Severe									
Preterm Rupture of Membranes	None									

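### For birth weight and preterm birth, two of five infant safety components, the plan compares the arms only on a yes/no cut and gives no difference or interval for the recorded grams and days

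*SAP*

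**What the plan says.** One primary safety endpoint is "Frequency and severity of adverse events specific to pregnancy, in pregnant women and their infants", to be described and compared between BOOSTRIX and Td (SAP 3.2.1; Protocol 3.2.1).

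SAP 9.5 implements this with proportions and Clopper-Pearson intervals (Tables 77 and 78), then Fisher's exact test for "the difference in the proportion of subjects reporting a pregnancy related adverse event" (Tables 79 and 80). Table 80 is titled "Comparison of the Proportion of Infant Subjects Experiencing Infancy-Related Adverse Events by Symptom and Treatment Group". Besides an any-event row it has five components: preterm birth, birth weight, neonatal complications in a term infant, other newborn AE, and congenital abnormality. Each gets a proportion, a difference with 95% CI, and a p-value. By the SAP Table 8 grading, a birth-weight event starts at 2500 g and a preterm event at 36 6/7 weeks. Table 79 has a matching maternal row for preterm contractions, labor or delivery.

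The measured values appear elsewhere. SAP 9.1 says that "birth weight, length at birth, and head circumference at birth, will be presented by treatment group and overall". Table 18, the "Summary of Infant Continuous Demographic and Baseline Characteristics by Treatment Group", gives mean, SD, median, minimum and maximum of birth weight (kg) and gestational age at delivery (days). It has no difference, interval or p-value. Vaccination takes place at 14 0/7 to 26 6/7 weeks.

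Three other displays are finer than yes/no, all without an arm difference: gestational-age categories (Table 17), size for gestational age (Table 76) and maximum severity grade (Table 82).

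**The concern.** Birth weight and gestational age at delivery follow vaccination in pregnancy, so they are outcomes of treatment. The plan nevertheless files their measured values under baseline characteristics. It makes inferences only about how many infants fall below a cut.

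A cut discards how far each infant lies from the threshold. If vaccination slightly lowered fetal growth or shortened gestation across all infants, the means could separate clearly while the counts below the cut differed by only a few. For these two components, the planned comparison would then say less about safety for the fetus and infant than the collected data could.

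**Working it through.** **Inputs from the documents.** "The study is planned to enroll 200 pregnant women (133 BOOSTRIX, 67 Td) and their infants" (SAP 5). For the test level, SAP 5 states "The calculations are based on a two-sided two sample T-test to compare means, with alpha = 0.05". That concerns the PT comparison. No level is stated for the safety tests, so two-sided 0.05 is assumed here.

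**Inputs not in the documents, therefore assumed and ranged.** Td low-birth-weight rate 3-20%; birth-weight SD 400-500 g; normal birth weight; a uniform shift toward lower weight in the BOOSTRIX arm.

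**The plan's own figure.** The only safety power stated is the chance of seeing at least one event within an arm, 1 − (1 − p)^n (SAP Table 3; Protocol Table 9). For p = 1% this gives 1 − 0.99^133 = 73.7% and 1 − 0.99^67 = 49.0%, as printed. The other entries also reproduce. The plan states no power for a between-arm safety comparison.

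**Step 1: the shift a t-test finds with 80% power.** The noncentrality is d × √(133 × 67 / 200) = 6.675d. Solving the noncentral t power for 80% gives d = 0.422 SD, which is 169 g at SD 400 g or 211 g at SD 500 g.

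**Step 2: the same shift seen through the cut.** With Td rate p, z = Φ⁻¹(p) and the BOOSTRIX rate is Φ(z + 0.422). Fisher power is exact, by enumerating all outcomes at 133:67. Information kept is φ(z)² / [p(1 − p)]. For p = 10%: z = −1.282, φ = 0.1755, and 0.0308 / 0.09 = 0.34.

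| Td rate | BOOSTRIX rate | Information kept | Fisher power | Ratio to 80% |
|---|---|---|---|---|
| 3% | 7.2% | 0.16 | 13.5% | 0.17 |
| 5% | 11.1% | 0.22 | 22% | 0.28 |
| 8% | 16.3% | 0.30 | 32% | 0.40 |
| 10% | 19.5% | 0.34 | 36% | 0.45 |
| 15% | 26.9% | 0.43 | 44% | 0.55 |
| 20% | 33.7% | 0.49 | 49% | 0.61 |

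**Step 3: fewer infants.** SAP 5 says "Prior experience suggests up to 15% of subjects may be excluded from the per protocol analysis for the primary immunogenicity outcome". That is not a safety loss, but as a sensitivity check 15% loss leaves about 113:57. The t-test then needs d = 0.458, and Fisher power at 8-20% is 30-50%, so the picture hardly changes.

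**Step 4: a different shape of harm.** Suppose only some infants are affected (simulation at 133:67).
- 15% of BOOSTRIX infants shifted by 3 SD, Td rate 5%: Fisher 73%, pooled t-test 63%, Welch 72%.
- 10% shifted by 3 SD, Td rate 15%: Fisher 23%, pooled 33%, Welch 41%.
- Over all cases tried (10-20% of infants shifted by 2-3 SD, Td rates 5-15%), Fisher has roughly 0.6-1.0 times the power of Welch.

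**Step 5: gestational age.** Assume mean 275 days, SD 10-14 days and a 5-day shift. With normal data, Fisher on birth before 259 days has 29-35% power and the t-test 66-91%. With strong left skew (skew-normal shape about −4), Fisher has 18-22% and Wilcoxon 69-92%. The direction is stable; the size depends on a skewness that the documents do not give.

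**The case against.** The strongest reply is that the analysis matches its endpoint. The endpoint is the frequency and severity of graded adverse events, and proportions and maximum grades by arm estimate exactly that. A difference in grams or days is an additional quantity. This stands: the graded rows should stay, and the added analysis should be called supportive.

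A second reply is that the study tests no specific null hypothesis (SAP 6.8) and claims no between-arm safety power, so a power benchmark is foreign to it. Protocol 11.4.2 expects few such events and reserves Fisher's test for when more than 5% of women are affected. But SAP 9.5 and Table 80 plan differences, intervals and p-values for the dichotomised versions without that condition. An estimation study has, if anything, more reason to report a mean difference with its interval.

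A third is that nothing is lost, because a reader can compute the mean difference and its interval from Table 18. That is true of the mean difference, after the fact. A Hodges-Lehmann estimate for skewed gestational age cannot be recovered from those summaries, and an analysis chosen later is open to selection.

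It is tempting to infer that a non-significant Table 80 row will be taken as proof of safety. The table also shows the difference with its 95% CI, so that misreading does not follow from the plan.

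**Conclusion.** The point holds for birth weight and preterm birth, two of the five infant components. Their only planned between-arm inference is on a yes/no cut, and the baseline label on the measured values is wrong whatever the power.

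Under a uniform normal shift at 133:67, the birth-weight cut keeps about 30-49% of the information at control rates of 8-20%. Fisher power is then 0.40-0.61 of the t-test's 80%, and 0.17-0.28 of it at rates of 3-5%. These figures rest on rates, SDs and an effect shape that the documents do not supply. The loss shrinks or disappears if harm falls on a subset of infants.

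A reader might infer that the infant part of the primary safety comparison has well under half the power the data allow. The documents do not support that. The other three components and infant SAEs have no continuous version, and the power ratio passes one half at control rates of 15% and above. Nor are the measured values unreported: they and finer categories are shown by arm, without inference. This is an inexpensive gain in precision on a primary safety question, not a failure of the endpoint analysis.

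**What to change.** In SAP 9.5, add two supportive safety analyses of BOOSTRIX versus Td:
- birth weight: difference in means with 95% CI, Welch t-test;
- gestational age at delivery in days: Hodges-Lehmann difference with 95% CI, Wilcoxon test.

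Report them beside Tables 78 and 80 as outcomes, and take both variables out of the baseline Table 18. Keep the graded low-birth-weight and preterm rows, which serve the endpoint and pick up harm confined to a subset.

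For scale, the half-width of the birth-weight interval would be about 1.972 × SD × √(1/133 + 1/67): 118 g at an assumed SD of 400 g and 148 g at 500 g.

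The values are already collected. The cost is SAP wording, one extra table, and two more unadjusted comparisons in a plan that adjusts for none.
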